10.0 Adverse Event (AE) Reporting and Monitoring

10.1 Adverse Event Characteristics

CTCAE term (AE description) and grade: The descriptions and grading scales found in the revised NCI Common Terminology Criteria for Adverse Events (CTCAE) version 4.0 will be utilized for AE reporting. All appropriate treatment areas should have access to a copy of the CTCAE version 4.0. A copy of the CTCAE version 4.0 can be downloaded from the CTEP web site:

Adverse event monitoring and reporting is a routine part of every clinical trial. First, identify and grade the severity of the event using the CTCAE version 4.0. Next, determine whether the event is expected or unexpected (see Section 10.2) and if the adverse event is related to the medical treatment or procedure (see Section 10.3). With this information, determine whether the event must be reported as an expedited report (see Section 10.4). Important: Expedited adverse event reporting requires submission of an AdEERS Multiple Agent Template found at [REDACTED]

10.11 Expedited reports are to be completed within the timeframes and via the mechanisms specified in Sections 10.4. All AEs reported via expedited mechanisms must also be reported via the routine data reporting mechanisms defined by the protocol (see Sections 10.52 and 18.0).

10.12 Each CTCAE term in the current version is a unique representation of a specific event used for medical documentation and scientific analysis and is a single MedDRA Lowest Level Term (LLT).

- **NOTE:** A severe AE, as defined by the above grading scale, is **NOT** the same as serious AE which is defined in the table in Section 10.4.

10.2 Expected vs. Unexpected

- The determination of whether an AE is expected is based on the agent-specific information provided in Section 15.0 of this protocol.
- Unexpected AEs are those not listed in the agent-specific information provided in Section 15.0 of this protocol.

NOTE: “Unexpected adverse experiences” means any adverse experience that is

neither identified in nature, severity, or frequency of risk in the information provided for IRB review nor mentioned in the consent form.

10.3 Assessment of Attribution

When assessing whether an adverse event is related to a medical treatment or procedure, the following attribution categories are utilized:

Definite - The adverse event is *clearly related* to the agent(s).

Probable - The adverse event is *likely related* to the agent(s).

Possible - The adverse event *may be related* to the agent(s).

Unlikely - The adverse event is *doubtfully related* to the agent(s).

Unrelated - The adverse event is *clearly NOT related* to the agent(s).

Events determined to be possibly, probably or definitely attributed to a medical treatment suggest there is evidence to indicate a causal relationship between the drug and the adverse event.

10.31 Special Situations for Expedited Reporting

Exceptions to Expedited Reporting: EXPECTED Serious Adverse Events

An expedited report or notification form may not be required for specific Grade 1, 2, 3 and 4 Serious Adverse Events where the AE is **EXPECTED**. Any protocol specific reporting procedures MUST BE SPECIFIED BELOW and will supersede the standard Expedited Adverse Event Reporting Requirements (Note: These adverse events must still be reported through the routine reporting mechanism [i.e. Nadir/adverse events form]; see footnote 1):

System Organ Class (SOC)	Adverse event/Symptoms	CTCAE Grade at which the event will not be expeditedly reported.
General disorders and administrations site conditions	Fatigue	Grade 3
Investigations	Malaise	
	White blood cell decreased	
	Platelet count decreased	Grade 3 and Grade 4
	Neutrophil count decreased	
Blood and lymphatic system disorders	Anemia	Grade 3 and Grade 4

1. These exceptions only apply if the adverse event does not result in hospitalization. If the adverse event results in hospitalization, then the standard expedited adverse events reporting requirements must be followed.

Specific protocol exceptions to expedited reporting should be reported expeditiously by investigators **ONLY** if they exceed the expected grade of the event, except in the event of a hospitalization (follow reporting instructions for section 10.4).

10.311 Persistent or Significant Disabilities/Incapacities

Any AE that results in persistent or significant incapacity or substantial

disruption of the ability to conduct normal life functions (formerly referred to as disabilities), congenital abnormalities or birth defects, must be reported immediately if they occur at any time following treatment with an agent under an IND/IDE since they are considered to be a serious AE and must be reported to the sponsor as specified in 21 CFR 312.64(b).

10.312 Death

- Any death occurring within 30 days of the last dose, regardless of attribution to an agent/intervention under an IND/IDE requires expedited reporting within 24-hours.
- Any death occurring greater than 30 days with an attribution of possible, probable, or definite to an agent/intervention under an NCI IND/IDE requires expedited reporting within 24-hours.
- **Reportable categories of Death**
 - Death attributable to a CTCAE term.
 - Death Neonatal: A disorder characterized by cessation of life during the first 28 days of life.
 - Death NOS: A cessation of life that cannot be attributed to a CTCAE term associated with Grade 5.
 - Sudden death NOS: A sudden (defined as instant or within one hour of the onset of symptoms) or an unobserved cessation of life that cannot be attributed to a CTCAE term associated with Grade 5.
 - Death due to progressive disease should be reported as **Grade 5 “Neoplasms benign, malignant and unspecified (incl cysts and polyps) – Other (Progressive Disease)”** under the system organ class (SOC) of the same name. Evidence that the death was a manifestation of underlying disease (e.g., radiological changes suggesting tumor growth or progression: clinical deterioration associated with a disease process) should be submitted.

10.313 Secondary Malignancy

- A **secondary malignancy** is a cancer caused by treatment for a previous malignancy (e.g., treatment with investigational agent/intervention, radiation or chemotherapy). A secondary malignancy is not considered a metastasis of the initial neoplasm.

- All secondary malignancies that occur following treatment with an agent under an IND/IDE must be reported via AdEERS. Three options are available to describe the event:
 - Leukemia secondary to oncology chemotherapy (e.g., Acute Myelocytic Leukemia [AML])
 - Myelodysplastic syndrome (MDS)
 - Treatment-related secondary malignancy
- Any malignancy possibly related to cancer treatment (including AML/MDS) should also be reported via the routine reporting mechanisms outlined in each protocol.

10.314 Second Malignancy

- A second malignancy is one unrelated to the treatment of a prior malignancy (and is NOT a metastasis from the initial malignancy). Second malignancies require ONLY routine reporting via CDUS.

10.4 Expedited Reporting Requirements:

FDA REPORTING REQUIREMENTS FOR SERIOUS ADVERSE EVENTS (21 CFR Part 312)

NOTE: Investigators MUST immediately report to the sponsor ANY Serious Adverse Events, whether or not they are considered related to the investigational agent(s)/intervention (21 CFR 312.64)

An adverse event is considered serious if it results in ANY of the following outcomes:

- 1) Death
- 2) A life-threatening adverse event
- 3) An adverse event that results in inpatient hospitalization or prolongation of existing hospitalization for ≥ 24 hours
- 4) A persistent or significant incapacity or substantial disruption of the ability to conduct normal life functions
- 5) A congenital anomaly/birth defect.
- 6) Important Medical Events (IME) that may not result in death, be life threatening, or require hospitalization may be considered serious when, based upon medical judgment, they may jeopardize the patient or subject and may require medical or surgical intervention to prevent one of the outcomes listed in this definition. (FDA, 21 CFR 312.32; ICH E2A and ICH E6).

ALL SERIOUS adverse events that meet the above criteria MUST be immediately reported to the sponsor within the timeframes detailed in the table below using the AdEERS Multiple Agent Template

Hospitalization	Grade 1 Timeframes	Grade 2 Timeframes	Grade 3 Timeframes	Grade 4 & 5 Timeframes
Resulting in Hospitalization ≥ 24 hrs		7 Calendar Days		24-Hour 3 Calendar Days
Not resulting in Hospitalization ≥ 24 hrs	Not required		7 Calendar Days	

NOTE: Protocol specific exceptions to expedited reporting of serious adverse events are found in section 10.31 of the protocol.

Expedited AE reporting timelines are defined as:

- “24-Hour; 3 Calendar Days” - The AE must initially be reported via paper Adverse Event Expedited Report – Single Agent or Multiple Agents within 24 hours of learning of the AE, followed by a complete expedited report within 3 calendar days of the initial 24-hour report.³
- “7 Calendar Days” - A complete expedited report on the AE must be submitted within 7 calendar days of learning of the AE.³

Serious adverse events that occur more than 30 days after the last administration of investigational agent/intervention and have an attribution of possible, probable, or definite require reporting as follows:

Expedited 24-hour notification followed by complete report within 3 calendar days for:

- All Grade 4, and Grade 5 AEs

Expedited 7 calendar day reports for:

- Grade 2 adverse events resulting in hospitalization or prolongation of hospitalization
- Grade 3 adverse events

Effective Date: May 5, 2011

10.42 General reporting instructions

The Mayo IND Coordinator will assist the sponsor-investigator in the processing of expedited adverse events and forwarding of suspected unexpected serious adverse reactions (SUSARs) to the FDA and IRB.

Use Mayo Expedited Event Report

form [REDACTED]

[REDACTED] for investigational agents or commercial/investigational agents on the same arm.

10.43 Reporting of re-occurring SAEs

ALL SERIOUS adverse events that meet the criteria outlined in table10.4 MUST be immediately reported to the sponsor within the timeframes detailed in the corresponding table. This reporting includes, but is not limited to SAEs that re-occur again after resolution.

10.5 Other Required Reporting

10.51 Adverse events to be graded at each evaluation and pretreatment symptoms/conditions to be evaluated at baseline per the CTCAE v4.0 grading unless otherwise stated in the table below:

System/Organ/Class (SOC)	Adverse event/Symptoms	Baseline	Each evaluation
Investigations	White blood cell decreased	X	X
	Neutrophil count decreased	X	X
	Platelet count decreased	X	X
Gastrointestinal Disorders	Diarrhea		X
	# of stools	X	
	Nausea	X	X
	Vomiting	X	X

10.52 Submit via appropriate MCCC Case Report Forms (i.e., paper or electronic, as applicable) the following AEs experienced by a patient and not specified in Section 10.51

10.521 Grade 2 AEs deemed *possibly, probably, or definitely* related to the study treatment or procedure.

10.522 Grade 3 and 4 AEs regardless of attribution to the study treatment or procedure.

10.523 Grade 5 AEs (Deaths)

10.5231 Any death within 30 days of the patient's last study treatment or procedure regardless of attribution to the study treatment or procedure.

10.5232 Any death more than 30 days after the patient's last study treatment or procedure that is felt to be at least possibly treatment related must also be submitted as a Grade 5 AE, with a CTCAE type and attribution assigned.

10.53 Refer to the instructions in the Forms Packet (or electronic data entry screens, as applicable) regarding the submission of late occurring AEs following completion of the Active Monitoring Phase (i.e., compliance with Test Schedule in Section 4.0).

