The study drug P1101 is a long acting pegylated interferon alpha-2b that has not yet been studied in MF. Preclinical safety data supports safe use of P1101 in humans. Clinical effects are expected to be similar to those of other approved Peg-IFN α products. Three clinical studies have looked at safety, efficacy, and maximum tolerated dose including one study in polycythemia vera patients. In this study, the MTD was found to be 540 μ g subcutaneously every two weeks. Among 34 evaluable patients, overall hematological response rate was 90% with complete response rates of 46% after one year of treatment. Sixteen serious adverse events have been reported. The incidence of treatment related emergent adverse events with P1101 was no higher than with Pegasys \circledR . Adverse events were mostly mild to moderate in severity and resolved spontaneously. Injection site erythema was the most common adverse event and headache was second.

Other reported adverse events included myalgia, decreased neutrophil count, back pain, increased body temperature, decreased white blood cell count, arthralgia, chills, fatigue, eye pain, feeling cold, nausea, transaminitis, somnolence, upper respiratory tract infection, feeling hot, decreased appetite, and pyrexia.

1.4

Rational

Patients with primary MF have a shortened life span and can have a significantly compromised quality of life as a result of progressive disease. Disease treatment earlier may delay progression of disease, prolong overall survival, and improve quality of life. We propose an open label nonrandomized pilot study of P1101 in patients with MF with the hypothesis that P1101 might have an impact in either early MF or in those with MF who are not eligible or failed ruxolitinib.

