2.2 Secondary

2.21 To evaluate the adverse event profile of P1101 in patients with myelofibrosis by cohort (early vs intermediate-2/high risk)

2.22 To evaluate the tolerability of P1101 in patients with myelofibrosis by cohort (early vs intermediate-2/high risk)

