15.15 Pharmacokinetic information: Mean P1101 serum concentration time curves were comparable across treatment groups and reached a peak at approximately 3 to 5 days after dosing and then declined gradually, with elimination half-lives of 60 to 118 hours. Single dose pharmacokinetic parameters (Cmax, AUC and AUC0-t) for P1101 increased with dose. The results of the power model analysis of dose proportionality for P1101 suggested more than proportional kinetics with increasing dose, as the slopes of the power model ranged from 1.19 to 1.36. The lack of dose proportionality for P1101 in this study may be attributed partly due to the high intersubject pharmacokinetic variability, and the small number of subjects.

15.16 Potential Drug Interactions: No information available.

15.17 Known potential toxicities: Adverse events reported most frequently (>10% of subjects) in either treatment in the *single dose* study include injection site erythema, headache, myalgia, decreased neutrophil count, back pain, increased body temperature, decreased white blood cell count, arthralgia, chills, fatigue, eye pain, feeling cold, nausea, increased alanine aminotransferase, somnolence, upper respiratory tract infection, feeling hot, decreased appetite, and pyrexia.

Adverse events reported in the *repeated dose* study have so far been mild to moderate. These include anemia, dizziness, dry mouth, dry skin, dyspnea, ear pain, epigastralgia, epistaxis, fatigue, fidget, flank pain, headache, myalgia, pruritus, respiratory distress, skin allergy, skin erythema, somnolence, sore throat, UTI, WBC decrease.

Investigators should also be informed of published data on marketed pegylated interferon. Subjects receiving *repeated doses* of interferon α -2b, have reported adverse events that include influenza-like symptoms, fever, headache, fatigue, rigors, musculoskeletal pain, arthralgia, back pain, injection site disorders (bruising, itching, and irritation), dry mouth, nausea/vomiting, diarrhea, abdominal pain, anorexia, weight, dizziness, impaired concentration, impaired memory, depression, anxiety/emotional lability/irritability, insomnia, alopecia, pruritus, dermatitis, rash, increased sweating, dyspnea, cough, and hypothyroidism. Common laboratory adverse events include neutropenia,

thrombocytopenia, increases in triglycerides and total cholesterol, abnormalities indicative of altered thyroid and liver function. Ten to fifteen percent of patients develop antibodies to interferon.

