16.32 Definitions and Analyses of Secondary Endpoints (Both Cohorts)

16.321 Survival time is defined as the time from registration to death due to any cause. The distribution of survival time will be estimated using the method of Kaplan-Meier (1958).

16.322 Adverse events: All eligible patients that have initiated treatment will be considered evaluable for assessing adverse event rate(s). The maximum grade for each type of adverse event will be recorded for each patient, and frequency tables will be reviewed to determine patterns. Additionally, the relationship of the adverse event(s) to the study treatment will be taken into consideration.

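### Grade 1 and not-related grade 2 events need not be submitted for 16 of the 19 terms listed at above 10% in the single-dose study, so the adverse event tables will understate low-grade toxicity

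*Combined protocol and SAP*

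**What the plan says.** **Collection.** Section 10.51 opens with "Adverse events to be graded at each evaluation and pretreatment symptoms/conditions to be evaluated at baseline per the CTCAE v4.0 grading". Its table marks six events for each evaluation: white blood cells, neutrophils, platelets, diarrhea, nausea and vomiting. Stool count is baseline only.

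Section 10.52 sets the rule for "the following AEs experienced by a patient and not specified in Section 10.51". The forms must carry "Grade 2 AEs deemed *possibly, probably, or definitely* related to the study treatment or procedure" (10.521), "Grade 3 and 4 AEs regardless of attribution to the study treatment or procedure" (10.522), and deaths (10.523). Section 10.11 adds that events reported by the expedited route must also go through routine reporting.

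**Known events.** Section 15.17 states: "Adverse events reported most frequently (>10% of subjects) in either treatment in the *single dose* study include injection site erythema, headache, myalgia", and goes on to 19 terms in all. A separate list gives 21 terms for the repeated-dose study. Section 1.3 says of P1101: "Injection site erythema was the most common adverse event and headache was second". It describes the events as largely of mild or moderate severity, without a breakdown by grade.

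**Use.** The secondary objectives are the adverse event profile (2.21) and tolerability (2.22: "To evaluate the tolerability of P1101 in patients with myelofibrosis by cohort (early vs intermediate-2/high risk"), both by cohort. Section 16.322 plans: "The maximum grade for each type of adverse event will be recorded for each patient, and frequency tables will be reviewed to determine patterns". Section 16.32 otherwise contains only survival time.

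**The concern.** The events chosen for grading at every visit overlap little with the events the protocol itself reports for P1101. Everything else passes through a severity and attribution filter before it must reach the database. An event that was present at grade 1 but not submitted looks the same in the 16.322 tables as no event, and 16.322 does not mention the filter.

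Three things are at stake:

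- The two secondary objectives rest on these data, for an agent that section 1.3 says had not been studied in myelofibrosis.
- Tolerability has no definition or analysis of its own in 16.32. That gap remains whatever the grade distribution turns out to be.
- Section 16.331 plans to correlate patient-reported symptoms with clinician-graded CTCAE symptoms. None of the six events in 10.51 is an MPN-SAF item. For overlapping symptoms such as fatigue, headache, itching and fever, the clinician side need not contain anything below related grade 2.

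Attribution adds to the problem. Fatigue, itching and fever are listed interferon effects in 15.17 and also disease symptoms scored by the MPN-SAF. In an open-label single-arm study, a grade 2 event ascribed to the disease need not be submitted. Section 16.42 plans to verify attribution only for grades 4 and 5.

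**Working it through.** The plan states no figure that can be reproduced on this point, so the check is a count followed by a sensitivity range.

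**Step 1: match the term lists in 15.17 to the table in 10.51.** Terms are counted as printed, so increased body temperature and pyrexia count as two.

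- Single-dose list: 19 terms, of which 3 are in 10.51 (neutrophils, white cells, nausea). Under the threshold: 19 − 3 = 16 (84%).
- Repeated-dose list: 21 terms, of which 1 is in 10.51 (white cells). Under the threshold: 21 − 1 = 20 (95%).
- Combined: five terms appear in both lists (fatigue, headache, myalgia, somnolence, white cells), so 19 + 21 − 5 = 35 distinct terms. Three are in 10.51. Under the threshold: 32 (91%).

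**Step 2: look for another source of the missing information.** On strict term matching, 7 of the 32 have one. ALT and hemoglobin come from scheduled laboratory tests; fatigue, headache, dizziness, itching and fever are MPN-SAF items. That leaves 32 − 7 = 25, among them injection site erythema, myalgia, arthralgia and chills. AST (laboratory) and depression (MPN-SAF), which are not in the two lists, are also covered. None of these sources supplies an attribution, and none arrives as a CTCAE grade.

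**Step 3: share of affected patients who would not appear.** For one event type, let g1 and g2 be the shares of affected patients whose maximum grade is 1 or 2, and r the share of grade 2 events judged at least possibly related. Then

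share not submitted = g1 + g2 × (1 − r).

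All inputs are assumptions. With 5% reaching grade 3 or higher, g2 = 0.95 − g1:

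| g1 | g2 | r = 1 | r = 0.75 | r = 0.5 |
|---|---|---|---|---|
| 0.30 | 0.65 | 30% | 46% | 63% |
| 0.50 | 0.45 | 50% | 61% | 73% |
| 0.70 | 0.25 | 70% | 76% | 83% |
| 0.90 | 0.05 | 90% | 91% | 93% |

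At r = 1 the loss is simply g1, so it exceeds half only if more than half of affected patients never pass grade 1. At r = 0.5 the loss is 0.475 + 0.5 × g1, which exceeds half once g1 is above 5%.

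**Step 4: the same range in patients.** Suppose an event affects half of the 19 patients, 9.5 on average (an assumption). The number appearing would lie between 9.5 × (1 − 0.30) = 6.7 and 9.5 × (1 − 0.925) = 0.7. A true 50% would be tabulated as anything from about 35% to about 4%.

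**The case against.** The strongest reply is that this is a deliberate submission threshold in a small pilot and contradicts nothing in the plan. Section 16.322 does not promise all-grade rates. The primary endpoint, the accrual suspension rule in 16.42 (related, grade 4 or higher, non-hematologic) and the triggers in Table 8.2 (grade 3 or higher) are untouched. All of that stands, and it limits the weight of the point.

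Several stronger readings are tempting, and the documents do not support them:

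- *That the rule drops the whole mild-to-moderate range, so the commonest effects will be largely missing.* Related grade 2 events are kept. For events attributed to P1101, only those that never exceed grade 1 are lost, and no grade split is given.
- *That grade 1 is never submitted.* Serious low-grade events, chiefly those with a hospital stay of 24 hours or more, reach the routine forms through 10.4 and 10.11.
- *That the 19 terms are established effects of P1101.* The list covers either treatment in that study, so some terms may have passed 10% only in the other treatment.
- *That diarrhea and vomiting have no place in 10.51.* They are in neither P1101 list, but 15.17 reports both for repeated interferon alpha-2b dosing, which is closer to this trial's schedule.
- *That section 1.2 identifies chronic low-grade toxicity as what limited interferon.* It says only that side effects limited use of the recombinant product, and it credits the pegylated alpha-2a form with better tolerability.
- *That the trial cannot show low-grade effects at all.* Section 16.331 analyses individual MPN-SAF symptoms, and laboratory results are submitted at each evaluation.

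The lack of a tolerability analysis is strictly a separate gap. It belongs here because no other planned analysis makes up for the thinned adverse event data.

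**Conclusion.** The point holds in a limited form. For 16 of 19 single-dose terms, and 32 of 35 across both lists, the forms need not carry grade 1 or not-related grade 2 events, apart from serious events carried over from expedited reporting. The 16.322 tables will understate low-grade incidence for those terms. This direction follows from the text alone, provided some affected patients stay at grade 1 or have grade 2 events judged not related.

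The size does not follow from the text. The range of about 30% to 93% rests on an assumed grade 1 share of 30% to 90%, a related share of grade 2 events of 50% to 100%, and 5% reaching grade 3 or higher. It is not a bound, and a smaller grade 1 share would give a smaller loss. A reader might infer that most cases will vanish; that would need data the documents do not contain.

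The laboratory and MPN-SAF data soften the loss for some terms but do not restore graded, attributed entries. Injection site reaction, myalgia, arthralgia and chills have no substitute source. The plan should be changed on this point, though no efficacy or stopping decision depends on it.

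**What to change.** 1. Add to the 10.51 table, at baseline and each evaluation and for all grades, at least injection site reaction, myalgia/arthralgia, fever/chills, headache and fatigue.
2. Derive CTCAE grades for ALT, AST and hemoglobin from the laboratory results already collected.
3. State in 16.322, and in the report, the submission threshold that applies to every other term, so that an absent entry is not read as an absent event.
4. Add to 16.32 a tolerability summary for objective 2.22: by cohort, the number and proportion of treated patients with P1101 reduced, omitted or held, or stopped for an adverse event, with exact confidence intervals, over a stated period. First confirm that the Evaluation/Treatment form in 18.1 records dose changes and their reasons, since its content is not shown.

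The cost is a few more form lines for at most 19 patients, some programming for the laboratory grades, and one paragraph in 16.32. Adverse event monitoring is already on the test schedule in section 4.0, so no visits are added. Reported adverse event rates will be higher, and the exact intervals will be wide with at most 6 and 13 patients per cohort.
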